4.1 Design

This study **aims** to determine the safety and feasibility of complete outpatient blinatumomab administration for subjects with MRD of B-precursor ALL using CWHMS to measure vital signs and transmit the vital signs to the HCP, mobile electronic devices (tablet) to electronically communicate with the HCP, and a Wi-Fi **and cellular** enabled platform for the transfer of data and communication between subject and HCP to detect clinically important changes. The data provided to the HCP will enable him/her to identify subjects at risk of developing grade 3 or 4 CRS, NT, or other SAEs requiring hospitalization during the MDMP. The HCP can then direct such subjects to the appropriate medical facility for hospitalization if needed.

During screening, subjects and caregivers will be trained on the CWHMS and assessed for compliance (Table 1-1-panel 1). Once enrolled, subjects will receive 2 complete cycles of blinatumomab in the outpatient setting in accordance with the monitoring and intervention guidelines (Table 1-1-panels 2 and 3).

After the end of cycle 2 clinical assessment visit, some subjects may continue to receive 2 additional (optional) cycles of outpatient blinatumomab. There will be no CWHMS outpatient monitoring during the optional cycles 3 and 4. For the purpose of this study, the MDMP is defined as the first 3 days of cycle 1 (72 hours) and the first 2 days of cycle 2 (48 hours) of blinatumomab infusion for subjects with MRD of B-precursor ALL.

The end of study visit will occur 30 days (+ 3 days) after the last dose of blinatumomab is administered (Figure 1-1).

This may coincide with the end of cycle 2 clinical assessment for subjects ending after cycle 2 or after cycle 3 or 4 if subjects and Pl's choose to receive the optional consolidation cycles 3 and/or 4.

The overall study design is described by a study schema in Section 1.2. The endpoints are defined in Section 3.

Date: 21 April 2022 Page 36 of 108

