The planned enrollment for this study is **approximately** 45 patients. The sample size is based on feasibility rather than on statistical considerations. Given a true probability of a primary endpoint event of 38%, the expected 95% upper confidence limit with 45 subjects would be 53.5%. The 38% subject incidence rate is based **on** the SAE rate in first 3 days of cycle 1 and first 2 days of cycle 2 from the previous MRD study (BLAST). Based on these assumptions, we expect to observe approximately 17 subjects who will experience the primary endpoint which should provide an initial indication of the timeliness of the therapeutic intervention when outpatient blinatumomab in administered in conjunction with remote digital monitoring.

Planned Analyses:

Interim Analyses: Safety data will be reviewed on an ongoing basis. A data review team (DRT), internal to Amgen but external to the study team, will assess safety after every fifth non-replaceable subject has been dosed and given an opportunity to complete MDMP. Refer to Section 4.2.1 for details on replacement of subjects.

Date: 21 April 2022 Page 17 of 108

Primary analysis: The primary analysis will occur when all subjects end the study.

Final Analysis: The primary analysis will also be the final analysis.

Descriptive statistics for demographic and safety will be summarized as appropriate. For categorical variables, the number and percentage of subjects in each category will be summarized. Continuous variables will be summarized by n, mean, standard deviation, median, Q1 (25th percentile), Q3 (75th percentile), minimum, and maximum values.

For a full description of statistical analysis methods, please refer to Section 9.

Statistical Hypotheses

No formal statistical hypothesis will be tested.

[figure not shown]
Sponsor Name: Amgen

Page 18 of 108 Date: 21 April 2022

1.2 **Study Schema**

Figure 1-1. Study Schema

ALL = acute lymphoblatic leukemia; CIVI = Continuous IV infusion; CR = Complete Remission; MRD = Minimal/Measurable Residual Disease

aScreening must be completed within 21 days of enrollment. Eligibility CR and MRD bone marrow assessments must be no more than 14 days prior to informed consent. Screening to establish digital health monitoring baseline must be completed within 7 days of enrollment. Digital Health monitoring devices will be tested for a minimum of 24 hours.

^B End of Cycle 2 clinical assessment to be performed on day 29 pf cycle 2.

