8.1.4 End of Study

All subjects will complete an end of study (EOS) visit approximately 30 (+ 3) days after the last dose of blinatumomab. If a subject starts a new treatment for their disease within 30 (+ 3) days of their last dose of blinatumomab therapy, an EOS visit should be conducted immediately prior to starting any new treatment, including HSCT conditioning regimens. Serious adverse events (and any concomitant medications associated with

Date: 21 April 2022 Page 55 of 108

SAEs observed by the investigators or reported by the subjects that occur within 30 (+ 3) days following cessation of treatment if the subject initiates new anticancer therapy (whichever is earlier) will be reported, followed, and recorded. End of study assessments will occur per the Schedule of Activities (Table 1-2). No digital tools will be provided by the study after cycle 2 day 2; subjects will continue with standard of care per investigator and site.

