For the purpose of this study, the mandatory device monitoring period (MDMP) is defined as the first three days of cycle 1 (72 hours) and the first 2 days of cycle 2 (48 hours) of blinatumomab infusion.

Therapeutic Intervention (TI)

Therapeutic intervention is any measurable action taken by the subject or performed on the subject as a result of the onset of the clinical parameters described. Such actions may include:

- Advised subject to go to hospital/ER immediately
- Advised subject to call 911 immediately
- Advised to suspend blinatumomab
- Advised to take antipyretic (e.g. acetaminophen)
- Advised subject to take dexamethasone
- Advised to suspend blinatumomab and take antipyretic
- Advised to suspend blinatumomab and take dexamethasone
- Advised to take other medication

• Other (if Other, describe the intervention)

Time to Therapeutic Intervention (TTI)

Time to therapeutic intervention is the time between the delivery of the device alert or unscheduled contact with HCP by subject/CG to report a change to the time of initiation of the therapeutic intervention.

TTI will be calculated as duration (in minutes) from time of the device alert (alarm triggered) to the time of initiation of the therapeutic intervention (i.e. when HCP silenced the alarm and advised an intervention).

If there is a case where the alarm is triggered, and the HCP advised an intervention, but event is not resolved and subject/CG presses the alarm again then that would be considered as a separate event (as alarm ID will be different) to calculate TTI.

TTI will be calculated for all the valid alarm triggers which leads to an intervention. If the calculated TTI is considered incongruous (i.e. more than 15min.) then a query will be entered in DIIR log.

All the scenarios defined below will be considered as invalid for calculation of TTI:

- If no intervention is required (e.g. technical issues) corresponding to an alarm.
- If intervention time is prior to the time of device alert (alarm triggered).

Treatment-emergent Adverse Event

Treatment-emergent Adverse Event is defined as adverse events starting on or after first dose of blinatumomab as determined by "Did event start before first dose of investigational product" equal to "No" or missing on the Events eCRF and up to the end of study visit.

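### Protocol Section 4.1 lets the end-of-study visit coincide with the C2D29 assessment, which is 29 to 33 days too early under the 30 (+3) day rule for a subject who completes cycle 2

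*Protocol*

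**What the plan says.** Protocol Section 4.1 (Design) gives the timing rule: "The end of study visit will occur 30 days (+ 3 days) after the last dose of blinatumomab is administered". The next sentence reads: "This may coincide with the end of cycle 2 clinical assessment for subjects ending after cycle 2". It goes on to place the visit after cycle 3 or 4 for subjects who take the optional cycles.

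The schema note in Protocol Section 1.2 dates the other visit: "End of Cycle 2 clinical assessment to be performed on day 29" of cycle 2. The Schedule of Activities (Table 1-2) agrees, and shows the end-of-cycle-2 assessment and the EOS visit as separate columns.

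Protocol Section 8.1.4 repeats the rule for everyone, "All subjects will complete an end of study (EOS) visit approximately 30 (+ 3) days after the last dose of blinatumomab", with one exception. If new treatment for the disease starts inside that period, "an EOS visit should be conducted immediately prior to starting any new treatment, including HSCT conditioning regimens".

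Protocol Sections 8.2.5.1.1 and 8.2.5.1.2 run AE and SAE collection through the EOS visit. SAP Section 5 counts adverse events as treatment-emergent from first dose "up to the end of study visit", and says that anything the site reports after that visit is not treatment-emergent.

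**The concern.** The two adjoining sentences of Section 4.1 cannot both be met by a subject who completes cycle 2 and starts no new therapy. This matters because the EOS visit is more than an appointment: it closes AE collection, SAE collection and the TEAE window.

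A site that used the permission in Section 4.1 would close safety collection at about the last dose for subjects stopping after cycle 2. Subjects going on to cycles 3 and 4 would still get their 30 days. Post-dose follow-up would then differ by treatment duration within the same summary tables.

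**Working it through.** **Inputs**
- Each cycle is 28 days of infusion and 14 days off (Protocol 4.3). The off period may be extended by up to 7 days (Protocol 1.1, Treatments).
- Day 1, hour 0 is the first dose (Protocol 8.1.2).
- The end-of-cycle-2 assessment is on C2D29 (Protocol 1.2 note; Table 1-2). Table 1-2 also has a cycle 2 column headed D29 ± 3 days.
- EOS is the last dose + 30 to 33 days (Protocol 4.1, 8.1.4, Table 1-2).
- After an interruption, total infusion time should still reach 28 days if possible (Protocol 6.5). Making up an interruption therefore only moves the last dose later.

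**Check of the cycle inputs.** 4 × (28 + 14) = 168 days; 168 / 30.4375 = 5.52 months. This reproduces the 5.5-month treatment period in Protocol 4.4.2.

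**Gap for a subject completing cycle 2**
1. An infusion of 28 × 24 hours from C2D1 hour 0 ends at C2D29 hour 0, so the last dose falls on D28 or D29 by calendar convention.
2. EOS runs from 28 + 30 = D58 to 29 + 33 = D62.
3. The gap to the assessment runs from 58 − 29 = 29 to 62 − 29 = 33 days.
4. In days from first dose, the assessment is at 42 + 28 = 70. EOS is at 70 + 30 = 100 to 70 + 33 = 103.
5. If EOS were held on C2D29, follow-up after the last dose would be 29 − 29 = 0 to 29 − 28 = 1 day, instead of 30 to 33.

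**Readings that might close the gap**

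| Reading | Gap in days |
|---|---|
| Assessment on D29 | 29 to 33 |
| Assessment anywhere from D26 to D32 | 58 − 32 = 26 to 62 − 26 = 36 |
| Assessment at the end of the 6-week cycle, D42 | 58 − 42 = 16 to 62 − 42 = 20 |
| The same with the 7-day extension, D49 | at least 58 − 49 = 9 |

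SAP Sections 3.1 and 7.2 print the EOS window as ± 3 days. Taking 27 days as the minimum moves the earliest EOS to 28 + 27 = D55. The smallest gaps in the four rows become 26, 23, 13 and 6 days, so none closes.

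**Working backwards.** C2D29 is 28 days after C2D1. To be 30 to 33 days after the last dose, that dose must fall at 28 − 30 = −2 to 28 − 33 = −5, that is, 2 to 5 days before C2D1. With the assessment on D32, the latest possible last dose is at 31 − 30 = +1, which is C2D2. Neither describes a subject who completed cycle 2.

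**What is exposed.** The monitored period (MDMP) ends 48 hours into cycle 2, well before C2D29, so the primary endpoint and time to therapeutic intervention cannot change. The summaries that use the whole TEAE window can: TEAEs and events of interest (SAP 9.6.2) and resource utilization (SAP 9.6.2 and 9.7.3).

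**The case against.** The strongest reply is that the intended design is clear. The 30-day timing is in the synopsis, the schema note, the Schedule of Activities and Protocol Sections 4.4.2, 7.2, 8.1.4 and 9.4.1.2, as well as the sentence just before the disputed one. Protocol Section 8 makes adherence to the Schedule mandatory. SAP Section 5 defines the EOS visit by the 30-day rule and does not repeat the coincidence sentence. A site would have to put one permissive sentence above all of these. This stands, and it makes the loss a risk rather than an expected outcome.

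The sentence also has a valid use. A subject moving straight from cycle 2 to conditioning or other new therapy could properly have both visits together under Section 8.1.4, and the schema note allows transplant at any time. A reader might infer that the visits can never coincide; Section 8.1.4 rules that out. What remains is that Section 4.1 extends the permission to every subject ending after cycle 2.

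A reader might also infer that about 30% of safety information would be lost, since 30 of roughly 100 days from first dose fall after the last dose. That is a share of calendar time, not of events. Protocol Section 2.3 says most adverse events arose in the first few weeks of cycle 1 and notes the drug's short half-life. The SAP tabulates subject incidence, so a later repeat of an event already counted adds nothing to its row.

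Some SAE capture would survive an early EOS visit. Suspected-related SAEs that come to the investigator's attention are still reported (Protocol 8.2.5.1.3), and Section 8.1.4 has an unclear clause on SAEs within 30 (+3) days. SAP Section 5 would still not count events reported after the visit as treatment-emergent.

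**Conclusion.** The point holds as an internal contradiction with a conditional consequence. For a subject who completes cycle 2 and starts no new therapy, the visit that Section 4.1 allows to serve as EOS comes 29 to 33 days before the EOS visit its own rule requires. No assessment window or cycle extension removes the gap. If a site relied on the sentence, post-dose follow-up for that subject would fall from about 30 days to 0 to 1 day.

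This assumes a 28-day cycle 2 infusion, and that the EOS date the site records is the one that closes the TEAE window.

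The documents do not support the stronger reading that TEAE and SAE incidence will be too low. They give neither the number of subjects stopping after cycle 2, nor how many sites would act on the sentence, nor the event rate after the last dose. The direction of any effect would be toward undercounting; its size cannot be stated. The exposure is limited to secondary descriptive summaries in a study with no hypothesis test. This is a minor point that is worth correcting because the correction costs almost nothing.

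**What to change.** Reconcile the Section 4.1 sentence with the 30 (+3) day rule in Section 8.1.4 and the Schedule of Activities. Either delete it, or limit it to subjects whose EOS visit is brought forward under Section 8.1.4 because new therapy or conditioning is about to start. Limiting it keeps the one valid use. The cost is one protocol sentence.

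Optionally, in SAP Section 5, end the TEAE window at last dose + 30 (+3) days, or at the start of new therapy if earlier, instead of at the visit. TEAE status would then not depend on when the visit was held. This costs one SAP sentence, plus conforming the statement about events reported after the visit. It cannot replace the protocol correction, because a wider analysis window does not recover events that were never collected.

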4.2 Number of Subjects

Approximately 45 adult subjects will be enrolled in the study, with MRD of B-precursor ALL in complete hematologic remission.

Subjects in this clinical investigation shall be referred to as "subjects." For the sample size justification, see Section 9.2.

4.2.1 Replacement of Subjects

Subjects will be replaced for analysis if the outpatient monitoring during blinatumomab infusion is not established.

Subjects removed from investigational product (IP) due to disease progression.

Replacement status is only applicable for internal data analysis.

4.2.2 Number of Sites

Approximately 25 investigative sites in the US will be included in the study. Sites that do not enroll subjects within 12 months of site activation may be closed.

4.3 Justification for Investigational Product Dose

The blinatumomab dosing regimen selected for this study is 28 μ g/day for subject's \geq 45 kg (or 15 μ g/m²/day to a max of 28 μ g/day for subjects < 45 kg) under continuous intravenous infusion (CiVI) for a period of 28 days per treatment cycle, followed by a 14-day infusion free interval, as per approved dosing.

4.4 End of Study

4.4.1 End of Study Definition

End of Study: The end of study date is defined as the date when the last subject across all sites is assessed or receives an intervention for evaluation in the study (ie, last subject last visit).

4.4.2 Study Duration for Subjects

For an individual subject the length of participation includes a 21-day screening period, up to a 5.5-month treatment period (assumes 2 complete cycles in the outpatient setting plus 2 additional optional cycles in the outpatient setting), and an end of study visit (30 days + 3 days after the last dose of study treatment).

For subjects who complete the protocol from the date of first dose through the end of study visit, the entire duration of the study will take approximately 8 months to complete.

Date: 21 April 2022 Page 37 of 108

5. Study Population

Investigators will be expected to maintain a screening log of all potential study candidates that includes limited information about the potential candidate (eg, date of screening).

Eligibility criteria will be evaluated during screening.

Before any study-specific activities/procedures, the appropriate written informed consent must be obtained (see Section 11.3).

Prospective approval of protocol deviations to recruitment and enrollment criteria, also known as protocol waivers or exemptions will not be provided.

5.1 Inclusion Criteria

Subjects are eligible for study participation only if all of the following criteria are met:

- Subject has provided informed consent prior to initiation of any study-specific activities/procedures OR subject's legally acceptable representative has provided informed consent prior to any study-specific activities/procedures being initiated when the subject has any kind of condition that, in the opinion of the Investigator, may compromise the ability of the subject to give written informed consent.
- 102 Age ≥ 18 years
- 103 **B-cell** precursor (**BCP**) ALL with minimal/measurable residual disease defined as hematologic CR with less than 5% bone marrow blasts and meets clinical eligibility criteria to receive blinatumomab as outlined below.
- 105 Hematologic criteria for remission as defined below:
 - < 5% bone marrow blasts.
 - Absolute neutrophil count ≥ 1.0 x10⁹ / L
 - Platelets ≥ 50 x10⁹/L (transfusion permitted)
 - Hemoglobin level ≥ 90 g/L (transfusion permitted)
- 106 Renal and hepatic function as defined below:
 - Total bilirubin < 3 x ULN unless related to Gilbert's or Meulengracht disease
 - Serum creatinine < 1.5 x ULN. If serum creatinine ≥ 1.5 x ULN, then
 measure Glomerular Filtration Rate (GFR); subject will be eligible only if
 measured GFR is within normal limits.
- 107 Eastern Cooperative Oncology Group performance status (ECOG PS) of 0 or 1.
- Negative pregnancy test in women of childbearing potential.
- Ability and willingness to wear and comply with the instructions for the use of and monitoring of the digital monitoring devices as outlined in informed consent.
- Subject resides within 1 hour of ground transportation to an advanced medical care facility for the duration of the MDMP

Date: 21 April 2022 Page 38 of 108

111 Adequate cellular service available during MDMP

Caregiver Eligibility Requirements

Presence of an adult (≥ 18 years) caregiver(s) in the same dwelling, for 24 hours/day for the entire MDMP. Caregiver will be expected to have access to transportation.

Ability and willingness to participate in the health management of the subject and to assist with the requirements of remote digital monitoring devices during the blinatumomab infusion within the MDMP

5.2 Exclusion Criteria

Subjects will not be eligible for study participation if any of the following criteria apply:

Disease Related

- 201 Presence of circulating blasts
- 202 Presence of extramedullary disease
- 203 History of relevant central nervous system (CNS) pathology or current relevant CNS pathology (seizure, paresis, aphasia, cerebrovascular ischemia/hemorrhage, severe brain injuries, dementia, Parkinson's disease, cerebellar disease, organic brain syndrome, psychosis, or coordination or movement disorders
- 204 Current infiltration of cerebrospinal fluid (CSF) by ALL. If screening CSF demonstrates leukemic blasts, subjects must receive intrathecal treatment and demonstrate negative CSF before enrollment and starting blinatumomab infusion.
- 205 Current autoimmune disease or history of autoimmune disease with potential CNS involvement
- 206 Allogeneic HSCT within 12 weeks before blinatumomab treatment
- 207 Active acute or chronic graft versus host disease (GvHD) requiring systemic treatment with immunosuppressive medication
- 208 Systemic chemotherapy within 2 weeks prior to study treatment (except for intrathecal prophylaxis)
- 209 Radiotherapy within 4 weeks prior to study treatment
- 210 Known hypersensitivity to blinatumomab or to any component of the product formulation
- Active malignancy other than ALL with the exception of basal cell or squamous cell carcinoma of the skin, or carcinoma in situ of the cervix.
- 212 History of other malignancy within the past 2 years, with the following exception[s]:
 - Malignancy treated with curative intent and with no known active disease present for ≥ 2 years before enrollment and felt to be at low risk for recurrence by the treating physician.
 - Adequately treated non-melanoma skin cancer or lentigo maligna without evidence of disease.
 - Adequately treated cervical carcinoma in situ without evidence of disease.

Date: 21 April 2022 Page 39 of 108

- Adequately treated breast ductal carcinoma in situ without evidence of disease.
- Prostatic intraepithelial neoplasia without evidence of prostate cancer.
- Adequately treated urothelial papillary non-invasive carcinoma or carcinoma in situ.
- 213 Currently receiving treatment with an investigational device or drug study or less than 30 days since ending treatment on an investigational device or drug study(ies)
- 214 Active uncontrolled infection requiring therapy
- 215 Known infection or chronic infection with hepatitis B virus (hepatitis B surface antigen [HBsAg] positive) or hepatitis C virus (HCV) (anti-HCV positive)
- 216 Known positive test for human immunodeficiency virus (HIV)
- Any concurrent disease or medical condition deemed to interfere with the conduct of the study and remote digital monitoring as judged by the investigator
- Any acutely ill cardiac patients with the potential to develop life threatening arrhythmias eg, very fast atrial fibrillation
- 219 Subjects with no cellular signal in their home
- Subjects with bi-lateral upper arm tattoos directly under the area of CWHMS application (**CH** wearable device)
- 221 Subjects with a known allergy to any of the device component materials
- Subjects with open wounds on both arms directly under the area of CWHMS application (**CH** wearable device) or with injuries to both arms
- Subjects with an upper arm circumference of less than 20 cm or greater than 50 cm
- 224 Subjects with an implantable defibrillator
- Subjects unwilling to wear the CWHMS (**CH** wearable device, axillary temperature patch) during the MDMP in cycles 1 and 2
- 226 Subjects with excessive scarring directly under the area of CWHMS (**CH** wearable device) application
- 227 Subjects who cannot have their BP measured in both arms (or wrists) eg due to atrio-venous shunt, risk of lymphedema or peripherally inserted central catheter line

Other Exclusions

- Female subject is pregnant or breastfeeding or planning to become pregnant or breastfeed during treatment and for an additional 48 hours after the last dose of protocol-specified therapy.
- Female subjects of childbearing potential unwilling to use 1 highly effective method of contraception during treatment and for an additional 48 hours after the last dose of protocol-specified therapy. Refer to Section 11.5 for additional contraceptive information.
- Female subjects of childbearing potential with a positive pregnancy test assessed at Screening by a serum pregnancy test and/or urine pregnancy test.

Date: 21 April 2022 Page 40 of 108

Subject likely to not be available to complete all protocol-required study visits or procedures, and/or to comply with all required study procedures (eg, PROs) to the best of the subject and investigator's knowledge.

